post-operative care in the recovery suite with routine recovery room vital checks. For participants who are randomized to the continuous pump group, the pump will be assembled and filled by pharmacy and attached to the previously placed catheter while the participant is in the recovery room. Once the participants are awake and alert in the recovery room, a study investigator will review the study specifics again, including the surveys with written information on the questions that will be asked. They will also be given written instructions on how to use the continuous pumps and how to remove it. If the patient is uncomfortable removing it themselves, they can come to the office to have it removed. For participants who received a continuous pump the investigator will go over the function of the pump, troubleshooting, and how to remove the pump at home. All participants will be discharged home from the recovery room after they have met the routine discharge criteria following existing standard of care recovery room protocols. The patient will also be contacted via telephone on post-operative day 1, 2, 3, 4 and 7 to assess for adverse events.

- All data will be recorded in an encrypted database which is HIPPA and IRB compliant. All participant information will be labeled with a participant study identification number with no identifiable information documented.

Procedures	In Office visit/schedule	Study Day 1, Day of Operation	Study Day 2 (POD 1)	Study Day 3 (POD 2)	Study Day 4 (POD 3)	Study Day 5 (POD 4)	Study Day 8 (POD 7)	Final Study Day, in office visit (POD 10-14)
Informed consent	X							
Demographics	X							
Medical history	X							
Randomization	X							
Administer study intervention		X						
Physical exam (including height and weight)	X	X						X
Preoperative Workup per standard protocol	X							
Pregnancy test ^b		X						
Adverse event review and evaluation	X		X X X X X					
MRI/Imaging assessment	X							
Online RedCAP Surveys (VAS, sleep disturbance, Opioid Consumption)	X	X X X X X X X X						

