16. WITHDRAWAL OF SUBJECTS

- *Describe anticipated circumstances under which subjects will be withdrawn from the research without their consent*
- *Describe procedures for orderly termination*
- *Describe procedures that will be followed when subjects withdraw from the research, including partial withdrawal from procedures with continued data collection.*

Participants may withdraw voluntarily from the study at any given time with no reason as is outlined in the informed consent for participation in the study. Any participant who withdraws from a study arm will still be contacted for follow-up assessments as outlined within this protocol unless the participant elects to forgo follow-up contact with the study assessors. This will include the surveys for outcome assessment, phone calls made on the subsequent postoperative days and the office visit following surgery.

Discontinuation from the continuous administration of local anesthetic prior to completion of the medications' dosing will not be deemed a withdrawal from the study but rather a discontinuation of treatment and the participant will continue to be followed up with for assessment of study outcomes with notation of the discontinuation of treatment within the database and the reason for discontinuation documented.

All participants who discontinue intervention will be followed in order to assess for potential adverse events, serious adverse events and any unanticipated problems pertaining to the use or administration of the study medications.

Adverse events include but are not limited to block failure, allergy to local anesthetic, persistent pain at injection/catheter site, local skin irritation at catheter site, pump/device failure.

Should a participant experience any of the serious adverse events listed in the next section, this participant will immediately be halted from their study intervention. These patients will be recommended to seek immediate care for assessment of their serious adverse event to best ensure patient safety. Should a patient experience an adverse event or unanticipated event, the study investigator who is contacted will determine if the participant's event meets criteria for discontinuation of treatment.

ADVERSE EFFECTS OF TREATMENT

Risks associated with single shot adductor canal block

1. Peripheral Nerve Injury

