1. Both anesthetists and surgeons recognize the benefits of peripheral nerve catheters (PNCs). The continuous infusion of local anesthetic near a peripheral nerve or plexus produces fewer systemic side-effects than i.v. opioids, increases postoperative patient satisfaction, and can allow for faster functional recovery of the operated limb.
2. Block Failure
 - a. Occasionally, there are instances when the catheter is passed easily but the nerve block fails to provide adequate anesthesia or analgesia.
 - b. This is rare with the use of ultrasound guidance and localization of the continuous catheter.
 - c. In the event of a block failure or inadequate placement that is not providing the patient any relief, the catheter will be removed either by the patient or post operatively depending on when it is discovered.
 - d. The practicing anesthesiologist will discuss with the patient the option of either trying a second time to place the catheter successfully in the post anesthesia recovery area or discontinuing the block altogether.
3. Accidental Catheter Migration/Removal
 - a. The incidence of accidental catheter removal is reported in the literature at about 1%. The use of sterile adhesive tagaderm dressing has been implemented to firmly secure the catheter to the skin to avoid migration or fall out. The dressing is checked to be secure after it has been applied.
 - b. In the event that the catheter is accidentally removed or dislodged during the course of the study, it should be removed and there will be no further intervention once the patient has been discharged home. The patient can place a Band-Aid over the catheter site and notify the coinvestigator or PI.
4. Localized Infection
 - a. Localized inflammation is infrequent (0–10%), and local infection (0–3%), abscess formation (0–0.9%), and sepsis occur even more rarely.
 - b. Transparent dressings are used to reduce the number of dressing changes while appropriately monitoring the site for signs of inflammation
 - c. Since the continuous catheter remains in for 48-72 hours, it does pose a theoretical increased risk of infection compared to a single shot adductor canal block although this has not been proven in the literature. To minimize this risk the site is prepped in sterile fashion with either chlorhexidine or iodine scrub. The injecting physician washes hands and uses sterile gloves and instruments for the course of this procedure.

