- b. Perioperative antibiotics will also be given which is standard protocol for ACL reconstruction regardless of catheter insertion or not.
- c. In the event that the patient notices any skin irritation, redness, foul smell, or drainage from the site of the injection, they will be advised to first call the safety officer, PI, or other co-investigator to describe their symptoms. The patients will also watch for fevers or chills. If infection is suspected they will be sent to the emergency room or surgeon's office for evaluation and further testing. They may be started on a course of oral antibiotics if an infection is concerning after evaluation.

Risks associated with continuous peripheral nerve catheter placement:

- 6. Both anesthetists and surgeons recognize the benefits of peripheral nerve catheters (PNCs). The continuous infusion of local anesthetic near a peripheral nerve or plexus produces fewer systemic side-effects than i.v. opioids, increases postoperative patient satisfaction, and can allow for faster functional recovery of the operated limb.
- 7. Block Failure
 - a. Occasionally, there are instances when the catheter is passed easily but the nerve block fails to provide adequate anesthesia or analgesia.
 - b. This is rare with the use of ultrasound guidance and localization of the continuous catheter.
 - c. In the event of a block failure or inadequate placement that is not providing the patient any relief, the catheter will be removed either by the patient or post operatively depending on when it is discovered.
 - d. The practicing anesthesiologist will discuss with the patient the option of either trying a second time to place the catheter successfully in the post anesthesia recovery area or discontinuing the block altogether.
- 8. Accidental Catheter Migration/Removal
 - a. The incidence of accidental catheter removal is reported in the literature at about 1%. The use of sterile adhesive tagaderm dressing has been implemented to firmly secure the catheter to the skin to avoid migration or fall out. The dressing is checked to be secure after it has been applied.
 - b. In the event that the catheter is accidentally removed or dislodged during the course of the study, it should be removed and there will be no further intervention once the patient has been discharged home. The patient can place a Band-Aid over the catheter site and notify the coinvestigator or PI.
- 9. Localized Infection

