18. RESEARCH RELATED HARM/INJURY

- *Describe the availability of medical or psychological resources that subjects might need as a result of anticipated problems that may be known to be associated with the research.*
- *If the research is greater than minimal risk, explain any medical treatments that are available if research-related injury occurs, who will provide it, what will be provided, and who will pay for it.*

Adverse events and planned interventions prior to discontinuation

- Failure of catheter placement despite successful administration of single site injection- any participant who was randomized to receive a continuous

pump, but the catheter was unable to be placed will be discontinued from the continuous pump protocol, however these patient's will continue to be followed according to the above stated protocol and their outcomes assessed in an intent-to treat manner based on their initial randomization.

- Continuous Block failure- if patient perceives no benefit from block but pump appears to be functioning patient will be requested to continue the pumps use until the medication dosing is completed, a perceived block failure will be documented.
- Allergy to local anesthetic- if a patient reports a systemic allergic response including but not limited to shortness of breath, diffuse rash, or angioedema the patient will be recommended to discontinue the intervention and seek emergency care. If the patient reports a local confined rash or skin irritation around the catheter site with no systemic symptoms the patient will be recommended to take a dose of Benadryl and apply a warm compress, if symptoms resolve the patient will remain in the study if there is no resolution the patient will be told to discontinue the medication administration and seek care for further evaluation.
- Persistent pain at catheter site- the patient will be advised to place a cold or warm compress at the catheter site and adjust the adhesive bandage if necessary if these interventions do not alleviate the participants pain within 12 hours the patient will be advised to discontinue the intervention.

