Pump/device failure- if the participant reports that the pump does not appear to be functioning properly the investigator who was contacted will assist the participant with troubleshooting the pump over the phone. If the investigator deems that the pump does not appear to be functioning after two independent attempts at troubleshooting/restarting the participant will be advised to discontinue the intervention at that time.

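### Sections 16 and 17 remove the catheter when the block gives no relief, Section 18 asks the patient to continue, and nothing says which case is which

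*Combined protocol and SAP*

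**What the plan says.** Three places deal with a continuous block that does not work.

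- **Section 16, Block Failure.** Item (a) describes the problem: "the catheter is passed easily but the nerve block fails to provide adequate anesthesia or analgesia". Item (c) gives the action: "In the event of a block failure or inadequate placement that is not providing the patient any relief, the catheter will be removed". Item (d) adds that the anesthesiologist discusses either a second placement attempt in the recovery area or stopping the block.
- **Section 17, Block Failure.** The same items are repeated. On who removes the catheter, and when: "the catheter will be removed either by the patient or post operatively depending on when it is discovered".
- **Section 18, Continuous Block failure.** "if patient perceives no benefit from block but pump appears to be functioning patient will be requested to continue the pumps use", and this holds "until the medication dosing is completed, a perceived block failure will be documented".

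Three other provisions bear on the point.

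- Section 18 treats a pump that does not work separately: if "the pump does not appear to be functioning after two independent attempts at troubleshooting/restarting the participant will be advised to discontinue the intervention".
- Section 16 lists block failure among the adverse events and says of such events that "the study investigator who is contacted will determine if the participant's event meets criteria for discontinuation of treatment". Later in the same section, safety is named as the main ground for stopping pump therapy.
- Section 11 says that, for patients with a pump, "the investigator will go over the function of the pump, troubleshooting, and how to remove the pump at home".

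**The concern.** The same report from a patient (catheter in, pump running, no relief) leads to removal under Sections 16 and 17 and to completion of the infusion under Section 18. The protocol names five hospitals, so staff at different sites could follow different sections.

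Two things are at stake. The first is how long the catheter and infusion continue after a reported failure. The protocol calls the added infection and toxicity risks of the catheter theoretical, and no added harm is claimed here.

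The second is consistent recording. Block failure is a listed adverse event, and Section 12 classifies each subject as having had any adverse event or none. If staff differ on whether a perceived failure is a block failure, a few subjects could be classified differently on that secondary outcome.

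**Working it through.** No figure in the plan depends on this point, so the check is mainly a comparison of the texts.

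**Step 1: set the instructions side by side.**

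| | Sections 16 and 17, item (c) | Section 18, Continuous Block failure |
|---|---|---|
| Trigger | Block failure or inadequate placement, no relief | Patient perceives no benefit |
| Pump condition | Not mentioned | Pump appears to work |
| Action | Catheter removed | Patient asked to go on |
| Endpoint of the action | On discovery | End of dosing |

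**Step 2: does the setting separate them?** No. Item (d) speaks of the recovery area, but item (c) allows removal by the patient, with timing that depends on discovery. That reaches past discharge. Section 11 confirms only that patients are taught to remove the pump at home; it does not mention block failure.

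**Step 3: does pump function separate them?** No. Section 18 distinguishes a working pump from a failed one. Item (c) makes no such distinction, so it also covers a working pump.

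**Step 4: does perceived versus established failure separate them?** It could, but the plan does not say how. Section 18 files its own case under block failure. Item (a) is the nearest thing to a definition, and it gives no pain threshold, time point, test or assessor. At home, absence of relief is known mainly from the patient's report, and that is also what triggers Section 18.

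**Step 5: does another clause decide?** No. The investigator's decision in Section 16 refers to discontinuation criteria, but none is given for block failure beyond the two conflicting instructions. The later clause on safety as the main ground refers back to the earlier text.

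**Step 6: size per affected patient.**

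Input: the catheter stays in for 48-72 hours (Sections 16 and 17). Let *t* be the hours from the start of the infusion to the report of no relief. The time that depends on the choice of section runs from max(0, 48 − *t*) to 72 − *t*.

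Section 11 schedules calls on postoperative days 1 and 2 but gives no clock times, so *t* is an assumption:

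- Day 1 call, *t* = 24: 48 − 24 = 24 to 72 − 24 = 48 hours.
- Day 1 call, *t* from 18 to 30: 48 − 30 = 18 to 72 − 18 = 54 hours.
- Day 2 call, *t* = 48: 48 − 48 = 0 to 72 − 48 = 24 hours.
- Day 2 call, *t* from 42 to 54: 0 (since 48 − 54 is negative) to 72 − 42 = 30 hours.

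These figures compare immediate removal with full completion. A patient who stops early, or who telephones before the scheduled call, would differ.

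**The case against.** The strongest reply is that the sections describe different situations. Sections 16 and 17 concern a finding about the catheter, followed by an anesthesiologist-led discussion in recovery. Section 18 concerns a patient's impression and deliberately records it as perceived. On that reading the fault is an undefined boundary, not a contradiction. Part of this stands: the wording does differ, and the authors may have intended the distinction. But removal by the patient extends beyond recovery, and no text draws the boundary, so the overlap remains.

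A second reply is that the plan has tie-breakers. The contacted investigator decides, safety is the main ground for stopping, the Section 18 list is headed as steps before discontinuation, the patient is only asked to continue, and anyone may withdraw. These narrow the gap without closing it. No stopping criterion for block failure is supplied. An instruction that runs to the end of dosing is also not an interim step. The neighbouring Section 18 items on local skin reaction, catheter-site pain (12 hours) and pump failure (two troubleshooting attempts) each state a route to stopping; this one does not.

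A third reply is that the hour ranges rest on assumed call times. That is correct. They illustrate the size and are not estimates from the plan. It is also fair that Section 17 repeats Section 16 and is not independent evidence.

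**Conclusion.** The concern holds and is minor. Two stated instructions lead to opposite actions for a patient at home with a working pump and no relief, and nothing in the plan says which applies.

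Few patients are likely to be affected. The protocol calls block failure rare without giving a rate, so no count is offered. For each such patient, 24-48 hours of catheter and infusion time is at issue at a day 1 call assumed at 24 hours, and 0-24 hours at a day 2 call assumed at 48 hours.

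The intention-to-treat assignment, the follow-up and the sample size of 39 per group do not change. The recording rules already allow the two routes to be told apart in the data: Section 16 requires discontinuation and its reason to be recorded, and Section 18 requires a perceived failure to be documented. The one outcome that could be touched is the any-adverse-event classification, through inconsistent labelling of block failure.

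**What to change.** The clinical investigators should do one of the following:

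1. Reconcile the block-failure items of Sections 16 and 17 with the Continuous Block failure item of Section 18, together with the Section 16 clauses on investigator decision and safety grounds, so that one instruction appears throughout.
2. If two situations are intended, state in each section which one it covers, and say how and by whom a perceived failure is distinguished from an established one.

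In either case, state whether a perceived failure counts as the block-failure adverse event, and check that the patient handout (not among the documents reviewed) says the same. Which clinical rule is right is for the investigators.

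The cost is wording in an amendment and a check of the handout, with no extra patients. The second option may also need the assessment to be recorded, for example as an item on an existing form.

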19. POTENTIAL BENEFIT TO SUBJECTS

- *Explain what benefits might be derived from participation in the study, noting in particular the benefit over standard treatment (e.g. a once-a-day administration instead of four times a day, an oral formulation over an IV administration).*
- *Also state if there are no known benefits to subjects, but detail the value of knowledge to be gained*

The idea is to evaluate the differences between 2 standard methods

1. To Compare the efficacy of two different modes of administration of peripheral nerve block for postoperative pain control after primary ACL reconstruction.
2. To compare the daily opioid consumption in patients, post operatively after ACL Reconstruction.
3. To determine the effectiveness of pain control and quality of sleep.
4. To compare patient satisfaction with their surgery based on method of pain control.

This will give us valuable information regarding our hypothesis that patients will have better pain control, satisfaction, sleep, and decreased opioid consumption with the use of a continuous infusion pump |

20. PROVISIONS TO PROTECT PRIVACY INTERESTS OF SUBJECTS

- *Describe the methods used to identify potential research subjects, obtain consent and gather information about subjects to ensure that their privacy is not invaded.*
- *In addition consider privacy protections that may be needed due to communications with subjects (such as phone messages or mail).*

a. *All of the patient's information that will be collected for the study will be uploaded to Northwell's secure REDCAP data collections system. Password access and encryption will help ensure that all patient information will be kept private. Strict recording processes and careful handling of data will be used to ensure there is no breach of data that has been recorded. After the study information has been recorded and the study is complete this information will be deleted. These measures will help maintain patient privacy.*

b. *Information that will be gathered from the surveys will be done by one of the coinvestigators that has been listed. The data variables that are recorded will be directly entered to Northwell REDCAP which is protected by user name and password. All of the co investigators will be in direct contact with the subjects and there won't be any intermediate passing off of the information to be recorded which decreases the handling of patient specific information and results.*

c. *Regarding identifying potential research subjects: The senior orthopedic surgery attendings participating in the study have been informed to contact us when they have a potential subject who is planning to have an ACL reconstruction when they have been seen in the office. There will be no marketing or recruiting used outside of patients that are undergoing this procedure with the orthopedic surgeon.*

Informed consent will be obtained in a private area to ensure the subjects' privacy is protected.

We have informed consent as attached, we will use encrypted data collection, Northwell REDCap, including the answers to surveys and phone calls, to protect their information.|

21. COSTS TO SUBJECTS

- *Describe any foreseeable costs that subjects may incur through participation in the research*
- *Indicate whether research procedures will be billed to insurance or paid for by the research study.*

No additional costs will be given to patients more than what they would be paying for their ACL reconstruction and perioperative pain management which are current routine procedures being done at all institutions.

